#### **Study Hypothesis:**

In patients with DC, FMT may improve liver functions, prevent complications, reduce levels of pro-inflammatory cytokines and lead to an improvement in prognostic scores (CTP, MELD, MELD Na) and 180-day survival.

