**Secondary Objective**

1. To assess and compare the changes in liver function in both groups based upon
  - CTP score at 28 days, 90 days and 180 days
  - MELD Score at 28 days, 90 days and 180 days
  - MELD Na Score at 28 days, 90 days and 180 days
2. To compare the complications in both groups in a follow-up period of 180 days
3. Changes in inflammatory markers (IL-1b, IL-6) in both groups at 28 days

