## **4. STATISTICAL ANALYSIS**

The results will be expressed as mean  $\pm$  standard deviation (SD) or median with range. Comparisons between groups will be performed using student's t-test or the Mann–Whitney U test. For categorical data chi-square test or Fisher's exact test will be applied. A value of  $P < 0.05$  will be taken as significant. The results will be analyzed at baseline and at day 7, 30 and 90 of the study. The in hospital survival curves will be made by the Kaplan-Meier method and compared with the log-rank test. All statistical tests will be done by Microsoft Excel and SSPSS Software version 18.

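### At least 12 secondary comparisons are each called significant at P<0.05, with no ordering, error control or exploratory label

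*Combined protocol and SAP*

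**What the plan says.** The Primary Objective is the difference in 180-day mortality between the FMT and standard-of-care groups. The Secondary Objective section then lists:

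- Three prognostic scores at three times each: "CTP score at 28 days, 90 days and 180 days", "MELD Score at 28 days, 90 days and 180 days", and MELD Na on the same schedule.
- Complications over 180 days of follow-up, with no list of which ones.
- Two cytokines at one time: "Changes in inflammatory markers (IL-1b, IL-6) in both groups at 28 days".

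The Statistical Analysis section gives generic tests: "Comparisons between groups will be performed using student's t-test or the Mann–Whitney U test", and "For categorical data chi-square test or Fisher's exact test will be applied". A single threshold covers everything: a value of P<0.05 "will be taken as significant. The results will be analyzed at baseline and at day 7, 30 and 90 of the study". Nowhere do the documents set an order among the secondary outcomes, adjust for their number, or describe them as exploratory. Sidedness is not stated.

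The Study Hypothesis combines the domains in one sentence: "FMT may improve liver functions, prevent complications, reduce levels of pro-inflammatory cytokines and lead to an improvement in prognostic scores", together with 180-day survival. The Study design paragraph calls the trial a pilot, and the sample size is 20 patients per arm.

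**The concern.** A 5% threshold limits the error of one comparison. Applied separately to a dozen, it does not limit the chance that at least one crosses by luck. The hypothesis covers several domains and the plan does not say how many must succeed, so an isolated significant score or cytokine could be presented as support for FMT without breaking any stated rule.

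This matters more because the primary comparison is weak. The documents give no death rate and no power calculation. For illustration, Fisher's exact test with 20 per arm has power of about 12% if mortality falls from 30% to 15%, 19% for 40% to 20%, and 27% for 50% to 25% (all rates assumed). If mortality is inconclusive, attention will naturally turn to the secondary results, which have no protection.

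**Working it through.** The plan states no family-wise error rate, so there is no figure to reproduce.

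**Count (Secondary Objective).** 3 scores × 3 times = 9; cytokines 2; complications at least 1. Total: 9 + 2 + 1 = 12 or more.

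**Level (Statistical Analysis).** 0.05 per test. Two-sided testing is assumed, so each test has 0.025 in the direction favouring FMT.

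**If the 12 tests were independent and FMT had no effect:**

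- At least one significant result in either direction: 1 − 0.95^12 = 46.0%.
- At least one favouring FMT: 1 − 0.975^12 = 26.2%.

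**With correlation.** The three scores overlap and are measured repeatedly, so independence gives the high end. The documents give no correlations, and those below are assumptions. Results come from a null simulation of two-sided t-tests with 20 per arm and 40,000 trials per setting.

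| Between scores | Between times | Between cytokines | Across domains | Either direction | Favouring FMT |
|---|---|---|---|---|---|
| 0.3 | 0.3 | 0.2 | 0.1 | 43% | 23% |
| 0.5 | 0.5 | 0.3 | 0.2 | 38% | 20% |
| 0.7 | 0.6 | 0.4 | 0.2 | 35% | 18% |
| 0.8 | 0.7 | 0.5 | 0.3 | 30% | 15% |
| 0.9 | 0.8 | 0.5 | 0.3 | 27% | 13% |

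The range is therefore 27% to 46% in either direction and 13% to 26% favouring FMT.

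**Sensitivity.**

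- Complications split into five separate tests (an assumption; 16 tests in all): 38% to 56% in either direction and 19% to 33% favouring FMT. The upper ends are 1 − 0.95^16 = 56.0% and 1 − 0.975^16 = 33.3%.
- Complications tested by Fisher's exact test: at 20 per arm its true two-sided size is 1.2% to 2.5% for event rates of 10% to 40%. Taking 2.48% for that one test, the independent figure falls from 46.0% to 1 − 0.95^11 × 0.9752 = 44.5%. Taking its half favouring FMT, 1.24%, the benefit figure falls from 26.2% to 1 − 0.975^11 × 0.9876 = 25.2%.
- One-sided tests at 0.05 towards benefit, which the plan does not state: the independent benefit figure would be 46%.

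**Which visits count.** The Statistical Analysis section names days 7, 30 and 90, while the objectives name days 28, 90 and 180. The count of 12 follows the objectives. The mismatch is a separate matter, but it leaves the set of tests undefined.

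**The case against.** The strongest reply is that this is a 20-per-arm pilot with one named primary outcome. Unadjusted secondary outcomes are common in such trials, and the secondary tests do not inflate the error of the mortality test. That stands, and it lowers the severity. It does not dispose of the point: the pilot label would be an answer if the plan called its secondary results exploratory, whereas it declares significance for them and states efficacy aims.

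Three stronger readings are tempting and should be resisted.

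- A reader might infer that an ineffective treatment would be credited with a benefit in 3 to 5 trials in 10. That is the rate of any significant difference, including differences favouring standard care. With two-sided tests the benefit figure is about half as large. It reaches 3 in 10 only with about 16 nearly independent tests or with one-sided tests at 0.05, and the plan specifies neither.
- A reader might infer that nothing is ranked at all. Mortality is ranked first; the missing order is among the secondary outcomes only.
- A reader might infer that the plan lets any one significant result confirm the hypothesis. The hypothesis is tentative and joins its elements with a conjunction, so it does not say that. The gap is that no sentence rules it out.

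It is also fair to say that the 16-test case is an assumption, because the kinds of complication appear in the Introduction and not as an outcome list. How results will be presented cannot be known either; the ethics annexure undertakes to report positive and negative results accurately.

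**Conclusion.** The point holds for the secondary outcomes. At least 12 comparisons share an unadjusted 0.05 threshold, with no order and no exploratory label. The false-benefit rate of 13% to 26% is roughly 5 to 10 times the 2.5% that a single two-sided test allows in that direction (0.13/0.025 = 5.2; 0.26/0.025 = 10.4). The figures rest on the count of 12, two-sided testing and the assumed correlations; only the count comes from the documents. Severity is minor to moderate: the plan's primary inference is unaffected, but what may be concluded from the secondary results is not controlled.

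**What to change.** In the Statistical Analysis section, state that 180-day mortality is the only confirmatory test. Report all secondary outcomes as exploratory estimates of the group difference with 95% confidence intervals and no significance claim. In the Study Hypothesis, add that no single secondary result confirms it.

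If a formal secondary claim is wanted, name one score at one visit as the lead and test it at 0.05. Test the others by Holm's procedure at 0.05 only if the lead is significant. This holds the error within the secondary family at 5%. Without that gate, the lead at 0.05 plus Holm on the other 11 leaves about 7% to 9% under correlated settings; under independence it is 1 − 0.95 × (1 − 0.05/11)^11 = 9.6%.

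The first option costs a few sentences, with no extra patients or data, and its downside is that fewer secondary results can be called significant. The formal route costs power: Holm's first step over 11 tests is 0.05/11 = 0.0045, and at 20 per arm a t-test's power for an illustrative 0.8 SD difference falls from 69% at 0.05 to 33%. For a pilot, estimates with intervals are the better choice.

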**Objectives:**

**Primary Objective:** To assess the difference in 180-day mortality between the FMT group and the SOC group.

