## **Study population**

All patients with decompensated cirrhosis who will be admitted to the Department of Hepatology in Medical Ward Unit or Liver ICU of Postgraduate Institute of Medical Education and Research (PGIMER) or will be attending the outpatient department of PGIMER during the period from August 2018 till May 2019 will be screened for eligibility for enrollment after ethical approval from the institute ethics committee. An informed consent will be taken from all the participants. Those patients who satisfy the inclusion and exclusion criteria and provide a valid informed consent will be enrolled in the study.

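### The primary objective is 180-day mortality, but the statistical section stops at day 90 and analyses survival only in hospital

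*Combined protocol and SAP*

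**What the plan says.** The primary objective is "To assess the difference in 180-day mortality between the FMT group and the SOC group". The Study Hypothesis likewise names "180-day survival". Among the secondary objectives, the scores are wanted at day 180 (for example "MELD Score at 28 days, 90 days and 180 days"), and so are complications: "To compare the complications in both groups in a follow-up period of 180 days".

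The Statistical Analysis section sets its analysis days in one sentence: "The results will be analyzed at baseline and at day 7, 30 and 90 of the study". Its only survival analysis is: "The in hospital survival curves will be made by the Kaplan-Meier method and compared with the log-rank test". It also has a general rule for categorical outcomes ("For categorical data chi-square test or" Fisher's exact test), which names neither mortality nor any day.

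Under Study population, recruitment covers inpatients and also patients who "will be attending the outpatient department of PGIMER".

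Follow-up is described twice. *Pre FMT* says the control arm is followed identically on days 7, 30 and 90, and gives both FMT and randomisation as the starting point. *Follow Up post FMT* gives days 7, 30, 90 and 180, counted from FMT.

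**The concern.** The two rules that govern the analysis, the list of days and the survival sentence, both miss the primary endpoint. A statistician following them would report death in hospital, or results up to day 90. Neither is the 180-day mortality difference.

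In-hospital survival cannot stand in for it. An outpatient has no index admission from which to count. For an inpatient, observation would end at discharge. Discharge is related to prognosis, so treating it as censoring would not recover 180-day mortality.

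Because no test is tied to the primary endpoint, the choice between a log-rank test and a chi-square or Fisher test stays open until the data are in. So does the choice of time origin. With 20 patients per arm, one or two deaths could make these choices matter. If time ran from FMT in one arm and from randomisation in the other, deaths between randomisation and FMT would drop out of one arm only.

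**Working it through.** The plan gives no figure to reproduce: the sample size of 20 per arm comes with no event rate, effect size or power. The check is a comparison of sections plus simple arithmetic.

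**1. What is required at day 180, and what is analysed**

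| Outcome | Where day 180 is required | Day-180 analysis listed in Statistical Analysis |
|---|---|---|
| Mortality | Primary Objective, Study Hypothesis | No |
| CTP score | Secondary Objective 1 | No |
| MELD score | Secondary Objective 1 | No |
| MELD Na score | Secondary Objective 1 | No |
| Complications | Secondary Objective 2 | No |

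None of the five is covered. This is a single omission, the missing day 180, with five consequences.

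**2. Share of the primary window after the last listed analysis day**

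(180 − 90) / 180 = 50%.

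This is a share of time, not of deaths. As an illustration only, assume a constant hazard and 180-day mortality m. Mortality by day 90 is then 1 − √(1 − m), and the share of 180-day deaths falling after day 90 is [m − (1 − √(1 − m))] / m.

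| Assumed m | Deaths by day 180, per 20 | Deaths by day 90, per 20 | Share after day 90 |
|---|---|---|---|
| 10% | 2.0 | 1.0 | 49% |
| 30% | 6.0 | 3.3 | 46% |
| 50% | 10.0 | 5.9 | 41% |

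The mortality range and the constant hazard are assumptions; the documents supply neither.

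**3. Time origin**

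*Pre FMT* gives pretreatment to patients already randomised to FMT: a 5-day antibiotic course, stopped at least 12 hours before the procedure. The interval from randomisation to FMT is therefore at least about 5 to 5.5 days.

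- 5 / 180 = 2.8%
- 5.5 / 180 = 3.1%

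Under the same constant-hazard assumption, expected deaths in the first 5.5 days per 20 patients run from 0.06 (m = 10%) to 0.42 (m = 50%). Control patients have no FMT date, so randomisation is the only origin both arms share.

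**4. Does the calendar allow 180 days?**

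The Methodology section ends recruitment in May 2019 and gives a 15-month study period ending in November 2019. For a patient randomised on 31 May 2019:

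- from randomisation: 31 May + 180 days = 27 November 2019, 3 days before the period ends;
- from FMT, with a lag of 5 to 6 whole days: 31 May + 185 or 186 days = 2 or 3 December 2019, 2 to 3 days after it ends.

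The same section also gives July 2018 to June 2020 for the study. On those dates neither origin overruns. The stop at day 90 is therefore not forced by the timetable.

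**The case against.** The strongest reply is that the document, read as a whole, contains the pieces. The objective fixes the endpoint, *Follow Up post FMT* schedules day 180 for patients in general, and death by day 180 is categorical, so the chi-square or Fisher rule at P < 0.05 could be applied. The section assigns tests by data type throughout, so the missing link may be drafting style.

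Part of this stands. Day 180 is not absent from the protocol, and it appears intended for both arms: the objectives need it in both, and *Management post FMT* uses that heading for both. A usable test family exists. But a scheduled visit is not an analysis. The section goes beyond silence: it states analysis days that end at 90 and a survival analysis confined to hospital.

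Four narrower points:

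- The 50% measures time, not lost deaths or bias. That is right, and no number of missed deaths is claimed.
- The bias from unequal clocks is conditional. No sentence says the arms use different origins, and the shift is small. It is a clarification, not the main defect.
- The log-rank test is not the only defensible choice. It compares whole curves and need not agree with the difference at day 180. Fisher's test on day-180 status would serve if vital status were complete. What is essential is that one test is named in advance.
- A telephone call gives vital status but not laboratory scores. That is correct; the scores need the day-180 visit.

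**Conclusion.** The concern holds and must be fixed. As written, the statistical section does not analyse the primary endpoint: its survival analysis has a different target, and its analysis days leave the last 90 of 180 days uncovered. This follows from the text alone and needs no assumed rate. The 41% to 49% share of deaths after day 90 is illustrative and rests on a constant hazard and assumed 180-day mortality of 10% to 50%. The actual loss cannot be computed from the documents. The time origin is secondary, at about 3% of the window.

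**What to change.** In the Statistical Analysis section:

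- Replace the in-hospital sentence with all-cause survival from randomisation to day 180, in all randomised patients by assigned arm, regardless of hospital status.
- Report Kaplan-Meier 180-day mortality per arm, with the difference and its 95% confidence interval.
- Name one primary test. The log-rank test, over days 0 to 180, is the natural choice because the section already uses it.
- State that patients lost to follow-up are censored at the date last known alive.
- Add day 180 to the analysis days, for the scores and complications as well as mortality.

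Reconcile *Pre FMT* and *Follow Up post FMT* so that both list day 180 for both arms, with vital status counted from randomisation.

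**Cost.** Wording changes in three sections and a day-180 vital-status check in every patient, by visit or call. The scores use the day-180 visit that *Follow Up post FMT* already schedules. No extra patients are needed. Counted from randomisation, the last patient finishes on 27 November 2019, inside the shorter study period.

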### **Inclusion Criteria**

1. 18-75 years
2. Confirmed advanced cirrhosis of any aetiology with a MELD score between 12 and 21.  
The diagnosis of liver cirrhosis will be based on clinical, radiological, or histological criteria
3. Patients must be deemed to have capacity to consent to study.

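### No mortality analysis is adjusted for baseline MELD, so with 20 patients per arm a chance MELD difference would bias the trial's mortality estimate

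*Combined protocol and SAP*

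**What the plan says.** The primary objective is "To assess the difference in 180-day mortality between the FMT group and the SOC group". The statistical section does not say which test serves it. It contains three statements that could bear on mortality:

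- On survival: "The in hospital survival curves will be made by the Kaplan-Meier method and compared with the log-rank test". The words "compared with the log-rank test" thus apply to in-hospital curves only.
- On proportions: "For categorical data chi-square test or Fisher's exact test will be applied".
- On timing: "The results will be analyzed at baseline and at day 7, 30 and 90 of the study". Day 180 is not in that list, although the follow-up section includes a 180-day visit.

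The threshold is P < 0.05, which "will be taken as significant". No regression model, strata or covariate appears anywhere in the section.

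On MELD, the inclusion criteria require "Confirmed advanced cirrhosis of any aetiology with a MELD score between 12 and 21", so a baseline value exists for every randomised patient. The study hypothesis is that FMT will "lead to an improvement in prognostic scores (CTP, MELD, MELD Na) and 180-day survival", which places MELD among the prognostic scores. Allocation is 1:1 from a random number generator, with no stratification, blocking or minimisation mentioned. The sample size is 20 per arm, in a study described as a pilot.

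**The concern.** The protocol treats MELD as prognostic and measures it on everyone at entry, but neither the allocation nor the analysis uses it. In a trial of 40 patients the arms can differ in mean MELD by a point or more through chance alone. An unadjusted mortality contrast then mixes that difference with the effect of FMT.

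Two things are at stake. The first is the estimate itself, which a later trial may draw on. The second is freedom of choice. The trial is open-label, and if an imbalance shows up, the question of adjusting will arise once the results are known. The plan does not propose adjusting after the fact, but it does nothing to settle the matter beforehand.

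**Working it through.** **The plan's own figure.** The only design figure is 20 per arm. It comes with no mortality rate, effect size or power, so it cannot be reproduced. The MELD spread, the hazard ratio per MELD point and the death rates used below are therefore assumptions, shown as ranges.

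**1. Chance imbalance in mean MELD.** The standard error of the arm difference is SD × √(2/20).
- SD 2.0: 2.0 × 0.316 = 0.63; 95% range ±1.96 × 0.63 = ±1.24 points; probability of a difference of at least 1 point 11%.
- SD 2.87 (flat over the whole numbers 12 to 21): 2.87 × 0.316 = 0.91; 95% range ±1.78 points; probability of at least 1 point 27%.
- The median absolute difference is 0.674 × SE: 0.43 and 0.61 points.

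**2. Shift in the hazard ratio.** The factor is approximately (hazard ratio per point) raised to the MELD difference.
- At the 95% limit: 1.10^1.24 = 1.13 to 1.20^1.78 = 1.38.
- At the median imbalance: 1.10^0.43 = 1.04 to 1.20^0.61 = 1.12.

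**3. Expected deaths.** With control mortality p and an assumed true hazard ratio of 0.5, FMT mortality is 1 − (1 − p)^0.5.
- p = 20%: 20 × (0.200 + 0.106) = 6.1 deaths.
- p = 50%: 20 × (0.500 + 0.293) = 15.9 deaths.

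**4. Effect on tests.** The simulation used 20 against 20, MELD flat on 12 to 21, complete follow-up to day 180 and 3,000 trials per setting. It compared the log-rank test with a Cox likelihood-ratio test adjusted for MELD. With no treatment effect, the rejection rates at a nominal 5% were:

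| Control mortality | HR per point | Log-rank, all trials | Adjusted, all trials | Log-rank, imbalance ≥1.5 | Adjusted, imbalance ≥1.5 |
|---|---|---|---|---|---|
| 20% | 1.1 | 4.9% | 6.0% | 4.8% | 6.0% |
| 20% | 1.2 | 5.6% | 7.2% | 7.1% | 6.5% |
| 40% | 1.1 | 5.2% | 5.5% | 6.5% | 5.1% |
| 40% | 1.2 | 4.6% | 5.1% | 9.1% | 4.6% |

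Imbalances of 1.5 points or more arose in about 10% of trials, so the last two columns rest on roughly 300 trials each. The 9.1% has a standard error of about √(0.091 × 0.909/285) = 1.7 percentage points.

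**5. Power at a true hazard ratio of 0.5, log-rank then adjusted.**
- 20% control mortality: 13.6% to 16.4% (HR 1.1 per point) and 11.7% to 15.0% (HR 1.2).
- 40% control mortality: 23.1% to 23.6% and 20.8% to 23.9%.

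Part of the gain at 20% mortality reflects the adjusted test's higher size.

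**6. Link between imbalance and estimate.** A separate simulation, also on assumed mortality and MELD effects, gave a correlation of 0.08 to 0.33 between MELD imbalance and the unadjusted log hazard ratio, and about zero after adjustment. Power rose there by about 1.5 to 5 points.

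**The case against.** Four objections carry weight.

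*The log-rank test is not the stated primary analysis.* A reader might infer that it is, since it is the only survival comparison named. The text does not support that: the sentence is confined to in-hospital curves, outpatients are also recruited, and nothing is assigned to 180-day mortality. This objection stands. The concern survives it, because chi-square and Fisher, the other candidates, are equally unadjusted.

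*Randomisation already protects the test.* A reader might infer that omitting MELD makes the mortality test invalid. It does not: log-rank size was 4.6% to 5.6% over all simulated trials. The harm is bias conditional on an imbalance, and the rise in size was marked only in the strongest setting.

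*Imbalance is small beside sampling error.* With 6 to 16 deaths, the standard error of the log hazard ratio is about 2/√D, or 0.82 to 0.50, so a 95% interval already reaches a factor of about 5.0 to 2.7 either way. Imbalance has an SD of ln(1.10) × 0.63 = 0.06 to ln(1.20) × 0.91 = 0.17 on that scale, between 0.06²/0.82² = 0.5% and 0.17²/0.50² = 11% of the variance. This stands as a limit on the benefit. It is not a reason to leave an avoidable bias in place.

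*Adjustment has its own costs, and this is a pilot.* The adjusted test runs slightly above 5% when deaths are few, and the adjusted hazard ratio is conditional on MELD, so it answers a slightly different question even under perfect balance. Both must be stated. Pilot status does not settle the matter, because the plan makes mortality the primary objective and sets a significance threshold.

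**Conclusion.** The point holds as a modest but worthwhile correction. The documents establish that no mortality analysis is adjusted for MELD, that every patient has a baseline value, that the protocol calls the score prognostic, and that no stratification is mentioned. They also leave the primary 180-day objective without an assigned test, which is the more basic gap and has to be closed first.

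The size rests wholly on the assumed MELD spread and hazard ratio per point. A material distortion is possible but is not the typical case, and the eligibility window limits how far the arms can drift apart. The documents do not support claims that the planned tests are invalid, or that adjustment would rescue a trial with this few deaths. The case for prespecifying MELD is that it removes imbalance bias and settles the choice before the data are seen.

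**What to change.** In the statistical analysis section:

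1. Name the primary analysis as time to death over 180 days from randomisation, in all randomised patients.
2. Prespecify a Cox model with arm and continuous baseline MELD as its only terms, and report the adjusted hazard ratio with its 95% confidence interval.
3. Report the unadjusted 180-day log-rank test alongside as a sensitivity analysis.
4. State that a penalised (Firth-type) fit will be used if an arm has no deaths or the estimates diverge.

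This takes a few sentences and uses data already collected. The costs should be stated in the plan:
- With roughly 6 to 16 deaths under the assumed rates, the interval is approximate.
- The adjusted test's size may be about 6% to 7% when deaths are few.
- The hazard ratio is conditional on MELD.
- The penalised fit may need software other than the Excel and SPSS version 18 that the section names.
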